## 10.2 Severity of Event

All AEs will be graded in severity according to the NCI Common Terminology Criteria for Adverse Events (CTCAE) Version 5.0 found at

[https://ctep.cancer.gov/protocoldevelopment/electronic\\_applications/ctc.htm#ctc\\_50](https://ctep.cancer.gov/protocoldevelopment/electronic_applications/ctc.htm#ctc_50)

If a CTCAE criterion does not exist, the investigator should use the grade or adjectives: Grade 1 (mild), Grade 2 (moderate), Grade 3 (severe), Grade 4 (life-threatening), or Grade 5 (fatal) to describe the maximum intensity of the adverse event.

## 10.3 Relationship to the Study Infusion

Association or relatedness to the study agent will be assessed by the investigator as follows:

- Definite: The event follows a reasonable temporal sequence from exposure to the investigational agent, has been previously described in association with the investigational agent, and cannot reasonably be attributed to other factors such as the subject's clinical state, other therapeutic interventions or concomitant medications; AND the event disappears or improves with withdrawal of the investigational agent and/or re-appears on re-exposure (e.g., in the event of an infusion reaction).
- Probable: The event follows a reasonable temporal sequence from exposure to the investigational agent and has been previously been described in association with the investigational agent OR cannot reasonably be attributed to other factors such as the subject's clinical state, other therapeutic interventions, or concomitant medications.
- Possible: The event follows a reasonable temporal sequence from exposure to the investigational agent, but could be attributable to other factors such as the subject's clinical state, other therapeutic interventions or concomitant medications.
- Unlikely: Toxicity is doubtfully related to the investigational agent(s). The event may be attributable to other factors such as the subject's clinical state, other therapeutic interventions, or concomitant medications.
- Unrelated: The event is clearly related to other factors such as the subject's clinical state, other therapeutic interventions, or concomitant medications.

For general AE assessment, an AE is considered related if it is assessed as definitely, probably, or possibly related; unrelated if it is assessed as unlikely related or unrelated.

#### **10.4 Monitoring and Recording Adverse Events**

Recording of adverse events will begin from the time of VIR-7831 infusion and continue to the end-of-study (week 36 follow-up call) for the participant. All SAEs will be followed through resolution or until return to baseline by a study physician.

Adverse events recorded in the appropriate case report forms include any SAE or Grade 2 or above Adverse Event. Information to be collected includes event description, date of onset, investigator assessment of severity, investigator assessment of relationship to study drug, date of resolution of the event, seriousness, and outcome. Any medical condition that is present at screening will be considered a baseline condition and will not be recorded as an AE unless there is worsening in the severity of the condition.

Abnormal laboratory values for laboratory parameters specified in the study should not be recorded as an adverse event unless an intervention is required (repeat testing to confirm the abnormality is not considered intervention), the laboratory abnormality results in a serious adverse event or the adverse event results in study termination or interruption/discontinuation of study treatment.

Adverse events will be assessed by the investigator or qualified designee. The investigator or relevant health care providers will attempt to establish a diagnosis of the event as indicated based on signs, symptoms and/or other clinical information. If the study team is informed of other unsolicited adverse events after the initial monitoring immediately after the infusion, evaluation will be similarly carried out.

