## 4.1 Overall Study Design

**Figure 1: Overview of study design and timeline.**

Participants will be screened, consented, and enrolled prior to transplant. Clinical evaluation will occur immediately prior to mAb administration. Participants will complete a weekly symptom questionnaire prior to and weekly after mAb administration for a total 36 weeks. Safety assessments will be performed with routine labs as part of standard stem cell transplant care. mAb will be administered intravenously within seven days of the start of conditioning, and the mAb will be infused at least 24 hours prior to the start of conditioning, i.e. mAb infusion will occur within 1-7 days prior to conditioning. Immediately prior to mAb administration (Pre), at the end-of-infusion (\* in the schematic), weekly up to week 4, monthly up to week 12, and at week 24 after mAb administration, blood will be collected by venipuncture or from a central venous catheter if one is available (10-20 mL per blood draw). At week 12, and monthly thereafter to the end of the primary end-point (week 24), blood will be self-collected using a TASSO device if the participant is unable to return for a venous blood draw. Each timepoint for blood collection will utilize two TASSO devices (or one TASSO+ device). If a participant can present in clinic or is in the hospital, blood collection by venipuncture or from a central venous catheter is permitted instead of using a TASSO device. Nasal specimens will be collected by mid-nasal foam swab at the same time-points as blood draws for antibody testing. Additional nasal swabs may also be collected off-schedule as needed based on reporting of respiratory symptoms on the weekly questionnaire, up to week 36. If positive for SARS-CoV-2, weekly nasal swabs will be obtained longitudinally for SARS-CoV-2 PCR until negative or until week 36. If a participant can present in clinic or is in the hospital, blood can be collected by venipuncture or from a central venous catheter instead of by a TASSO device. Routine nasal swabs collected as part of standard clinical care for SARS-CoV-2 surveillance by PCR post-transplant are not shown. At week 36 (not shown), participants will receive a follow-up phone call to assess for the development of antibody dependent enhancement if they had COVID-19.

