## 4.2 Protocol Enrollment

Enrollment is expected to take approximately 6-12 months. The duration of a participant's involvement with the study is expected to be approximately 24 weeks for the primary end-point with a follow-up call at week 36 to assess for antibody dependent enhancement. The study will be introduced to HCT candidates during intake or at transplant arrival at which time interested participants can contact the study team to discuss participation and to schedule a screening visit.

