
Antibody-dependent enhancement of disease and anti-drug antibodies have not been observed *in vitro*, in animal models, or in clinical studies thus far with VIR-7831(25, 26). Participants will receive a phone call at week 36 to monitor for the development of antibody-dependent enhancement of disease. There is currently no available PK or immunogenicity data on a 2000 mg IV dose. Since sotrovimab exhibits dose proportional PK, exposures would be expected to be dose proportional between a 500 mg and 2000 mg IV doses. In the GLP repeat dose IV monkey toxicology study there were no toxicity findings at doses up to 500 mg/kg, the highest dose tested and the no-observed-adverse-effect-level (NOAEL). Assuming dose proportional increase in exposures at 2000 mg, sotrovimab Cmax and area under the curve (AUC) in patients are expected to be 15.5 and 13.5-fold lower than Cmax and AUC values from the toxicology study at the NOAEL, therefore, supporting the evaluation of sotrovimab at the higher clinical dose of 2000 mg IV. Sotrovimab is also considered low risk for immunogenicity based on intrinsic product characteristics (i.e., quality of GMP manufacturing controls and release specifications), extrinsic factors (i.e., administered as a single dose) and patient population (i.e., no apparent heightened risk of immune response). Limited preliminary analysis of immunogenicity data through Day 29 is available from 391 and 38 subjects given 500 mg IV in COMET-ICE and Japan-PK studies, respectively. To date, the incidence of treatment-emergent ADA responses has remained low, with no detectable impact on safety or efficacy. These clinical findings align with the low immunogenicity risk profile and the risk

prediction would not be expected to change substantially at higher doses when the product is administered as a single dose by the same route.

Drawing blood is a routine part of transplant care but can cause bleeding, bruising, pain, soreness, redness, swelling, itching, and/or muscle damage at the site where blood samples are taken. Rarely an infection at the site where blood samples are taken may occur or a blood clot may form. There is also the risk of fainting, dizziness, and anemia (low numbers of red blood cells).

Nasal swab sampling can result in discomfort or pressure during the procedure.

There may be risks of loss of privacy and confidentiality. All blood and swab samples will be given a code and stored securely.

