### Medical records:

Medical records from the University of Washington, outside health care providers, and databases maintained by the Fred Hutchinson Cancer Center will be reviewed for data such as subjects' demographics, underlying malignancy, treatment, and medical history with a focus on HCT related treatment and disease response.

- At screening, these include review of standard pre-transplant medical history and labs to assess inclusion/exclusion criteria:
  - Age
  - Underlying disease
  - HCT planned type and date
  - History of prior transplants

- History of COVID-19, positive PCR of a respiratory specimen for SARS-CoV-2 as long as it is not within four weeks from conditioning, or seropositivity for SARS-CoV-2
  - History of SARS-CoV-2 infection or vaccination of the donor
  - Ability to provide informed consent
  - Prior administration of IVIG
  - Pregnancy test results
  - Previous known allergies to any component of VIR-7831
  - Previous anaphylaxis or severe hypersensitivity reaction, including angioedema, to a mAb
  - Participation in other clinical studies that preclude the use of other investigational compounds
- On the day of infusion, at the end-of-infusion, weekly to week 4, and monthly to week 24, these include review of the medical history with regards to underlying disease, medications, history of infections, history of vaccinations, and presence/severity of GVHD. In addition, standard post-transplant laboratory testing which are collected as follows from Day 0 to +100 post-transplant and as clinically indicated thereafter will be reviewed, including:
  - CBC daily until granulocytes > 500 cells/mm^3 and platelets > 20,000 cells/mm^3, then a CBC a minimum of once weekly until 100 days post-transplant.
  - Electrolytes, glucose, creatinine, BUN, every day as inpatient. At the ambulatory clinic, electrolytes are monitored a minimum of once per week.
  - Ca++, Mg++, PO4, albumin, twice a week as inpatient. At the ambulatory clinic, they are monitored a minimum of once per week
  - Bilirubin [total/direct], AST, alkaline phosphatase, LDH, a minimum of two times a week as inpatient. At the ambulatory clinic, monitoring is as follows: – If LFT's elevated: twice weekly.
  - INR is monitored weekly for patients on prophylactic Warfarin.
  - Blood cultures (aerobic and anaerobic) are obtained from patients receiving > 0.5 mg/kg/day of prednisone or prednisone equivalent. Twice weekly when inpatient.

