#### **Reporting to GSK and Vir**

- Any SAE, regardless of the causal relationship to Study Drug, occurring after the Subject has signed the Informed Consent Form through study end should be reported to the drug-sponsor (Vir/GSK) (safety mailbox provided below), no more than 24 hours after SAE awareness.
- All other events of special interest, including reports of pregnancy, abuse, misuse, medication error, overdose, and occupational exposure are to be captured using the SAE procedures but are to be considered as SAEs only if they meet serious criteria. All events of these types should be reported to Vir and GSK, regardless of whether or not there is an associated AE or SAE, no more than 24 hours after awareness.
  - If a pregnancy is reported during the study period, pregnancy information will be recorded and submitted to Vir/GSK within 24 hours of learning of the female participant pregnancy. While pregnancy itself is not considered to be an AE or SAE, any pregnancy complication or elective termination of a pregnancy for medical reasons will be reported as an AE or SAE.
  - The participant will be followed to determine the outcome of the pregnancy and for up to 1 year after birth. The investigator will collect follow-up information on the participant and the neonate/child and the information will be forwarded to Vir/GSK.
- Follow-up information to all initial reports will be sent to Vir and GSK no more than 24 hours after awareness.
- SAE reports and pregnancies shall be sent to GSK CMG via email at [[contact]](mailto:[contact]) or alternatively faxed to [[name]]([contact]) if email is unavailable.

- Adverse Events of grade 2 or higher severity and Unexpected Adverse Events that are not attributable to the underlying disease for which HCT was performed, or not attributable to graft-versus-host disease (GVHD), not attributable to complications of immunosuppressive medications, and which is different from what is expected in the clinical course of a HCT recipient will also be reported to Vir Biotechnology at least annually.

**Reporting to IRB:** The investigator or designee must report events to the FHCRC IRB in accordance with the policies of the IRB.

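### Adverse events are to be recorded to week 36, but scheduled chart review ends at week 24 and no active collection is defined for the last 12 weeks

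*Combined protocol and SAP*

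**What the plan says.** **Window.** Section 10.4 states: "Recording of adverse events will begin from the time of VIR-7831 infusion and continue to the end-of-study (week 36 follow-up call"). The case report forms take any SAE and any event of Grade 2 or above.

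**Chart review.** The medical-records part of Section 9.1 schedules it as follows: "On the day of infusion, at the end-of-infusion, weekly to week 4, and monthly to week 24, these include review of the medical history". Underlying disease, medications, infections, vaccinations and GVHD are all reviewed on that schedule. Standard laboratory tests are collected "as follows from Day 0 to +100 post-transplant and as clinically indicated thereafter will be reviewed".

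**Week-36 call.** It is described three times:
- Section 4.1: "participants will receive a follow-up phone call to assess for the development of antibody dependent enhancement if they had COVID-19".
- Section 4.2 puts participation at "approximately 24 weeks for the primary end-point with a follow-up call at week 36 to assess for antibody dependent enhancement".
- Section 7: "Participants will receive a phone call at week 36 to monitor for the development of antibody-dependent enhancement of disease".

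**Symptom questionnaire.** The synopsis and the questionnaire part of Section 9.1 give a total of 24 weeks. Section 4.1 gives a total of 36 weeks. Section 9.1 describes an online form covering many body systems.

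**Other routes.** Section 6.1.3 asks participants to contact the team about later events. Section 10.4 has the team evaluate unsolicited events of which it is informed.

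**Start of the window.** Section 10.4 begins at infusion. In Section 10.4.1, SAE reporting to the drug sponsor covers any SAE "occurring after the Subject has signed the Informed Consent Form through study end".

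**The concern.** The stated recording window is longer than the stated schedule for finding events. Up to week 24 a staff member opens the chart at set times and can find a hospitalization, diagnosis or death that nobody reported. After week 24 no such review is scheduled, and the one later contact named as the end of recording has a narrower stated purpose.

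Several features of this trial make the late period worth covering:
- Section 2 says patients are followed less closely by the transplant service after day +100, so the team is less likely to hear of an event by chance.
- Section 7 says no PK or immunogenicity data exist for the 2,000 mg intravenous dose.
- Section 12.3 anticipates a half-life of up to 3 months and expects any breakthrough infection particularly towards the end of the study.
- Section 10.1 ties death and hospitalization as SAE criteria to a protocol-defined surveillance period. If surveillance after week 24 is unclear, so is whether such events qualify.

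Safety monitoring is a secondary objective. A summary over 36 weeks would combine two intensities of ascertainment without saying so.

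**Working it through.** The plan states no figure for this point, so there is none to reproduce. The check compares the window with each source of events.

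**Length of the gap.** Inputs: end of recording, week 36 (Section 10.4); last scheduled chart review, week 24 (Section 9.1).
- Gap = 36 − 24 = 12 weeks = 12 × 7 = 84 days.
- Share of the window = 12 / 36 = 33.3%.

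**Each source in weeks 24 to 36.**

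| Source | Where stated | Reaches week 36? | Stated use for general AEs or SAEs? |
|---|---|---|---|
| Chart review | Section 9.1 | No, ends at week 24 | It reviews medical history, infections, medications and GVHD |
| Scheduled laboratory tests | Section 9.1 | No, day +100 and then as indicated | Routine safety tests |
| Symptom questionnaire | Synopsis; Sections 4.1 and 9.1 | 24 or 36 weeks, contradictory | None stated. It triggers samples for nose or chest symptoms (9.1) and assesses diarrhea (12.2) |
| Symptom-triggered and follow-up swabs | Sections 4.1 and 9.1; Appendix A notes | Yes | SARS-CoV-2 only |
| Week-36 call | Sections 4.1, 4.2 and 7 | Yes | Antibody-dependent enhancement only |
| Participant contacts the team | Sections 6.1.3 and 10.4 | Yes | Yes, but passive |

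**Laboratory schedule on the infusion clock.** Day +100 counts from transplant. The documents do not fix the interval from infusion to transplant. Assuming 1 to 21 days, day +100 falls between (100 + 1)/7 = 14.4 and (100 + 21)/7 = 17.3 weeks after infusion, which is before week 24 throughout that range.

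**Two readings of the questionnaire.**
1. If it stops at week 24, nothing is scheduled for all participants between week 24 and the call.
2. If it runs to week 36, there is weekly symptom reporting in the gap but still no scheduled chart review. The questionnaire-triggered swabs to week 36 fit this reading. However, no passage sends its answers to the adverse event forms or says that it asks about hospitalizations or diagnoses, and a participant-completed form cannot report a death.

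Under both readings the 12-week gap in chart review stands, and so does the lack of a defined active method. The week columns of Appendix A are incomplete in the text available, so nothing is inferred from them.

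**Delay.** An SAE just after the week-24 review that no other route brings to light could stay unknown for up to 36 − 24 = 12 weeks, or longer if it is a death and the call goes unanswered. This is a worst case.

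**The case against.** The strongest reply is that a reader might infer that the last third of the window has no scheduled ascertainment at all, and the documents do not support that. Section 4.1 runs a multi-system weekly questionnaire for 36 weeks, and the call is itself scheduled and named in Section 10.4 as the end of recording. Sections 4.2 and 7 attach no COVID-19 condition to the call. In Section 4.1 the condition may qualify the assessment rather than who is called. This part of the objection stands. The gap is in scheduled chart review and in a defined method, not in all contact.

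Oversight continues as well. Section 13.1 gives the Principal Investigator continuous review of safety, and Section 13.2 has at least weekly meetings on recently acquired data and events. Section 11 allows safety outcomes to be taken from the electronic record even after withdrawal from study activities. These provisions make late capture possible. They set no schedule for looking, and they review what has already been acquired.

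The FDA and drug-sponsor reporting clocks in Section 10.4.1 run from awareness, so late discovery breaches no stated deadline. That is correct. The cost is later knowledge, not non-compliance.

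On the start date, recording and drug-sponsor reporting can properly have different windows. Section 10.4.1 also puts SAEs on an SAE form without an infusion limit. A reader might infer that SAEs between consent and infusion are lost to the study, but the text does not show this. Only a minor alignment point remains.

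**Conclusion.** The point holds as a mismatch between the safety window and the schedule that serves it. For 12 of 36 weeks (33%) no chart review is scheduled and no active collection of general adverse events is defined. The documents also contradict themselves on whether the questionnaire covers those weeks. Events in the period may be under-counted or learned of late.

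The 33% is a share of time. A reader might take it as the share of events missed, or as the understatement of a 36-week rate. Either would need a constant event rate and no capture at all after week 24. The documents give no event rate, describe the early post-transplant period as the most vulnerable for infection, keep passive routes open, and define no 36-week rate. The size of the loss therefore cannot be computed from them.

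The conclusion assumes that unstated content (general adverse event questions on the call, or a link from questionnaire to case report form) is not planned elsewhere. It is more than a missing detail, because the stated review schedule stops short of the stated window. The change should be made. It affects safety capture and not the primary pharmacokinetic analysis.

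**What to change.** - **Section 9.1, medical records:** add at least one review at week 36 covering weeks 24 to 36.
- **Section 4.1:** state that the week-36 call goes to every participant and asks about all SAEs and Grade 2 or higher events since week 24, as well as antibody-dependent enhancement. Make Sections 4.2 and 7 agree.
- **Synopsis, Sections 4.1 and 9.1:** reconcile the questionnaire duration.
- **Section 10.4 (minor):** align the SAE start (infusion) with Section 10.4.1 (consent), or state that the two windows differ by intention.

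The cost is one extra chart review per subject and a few questions on a call already planned, both by existing staff.

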**FHCC Patients: Emergency (24-hour) [contact]; [contact]**

**24-Hour [contact] (Ask for the Infectious Disease fellow On-Call)**

**UW Medical Center Patients: Paging Operator [contact] and ask for [name]**

## PROTOCOL SYNOPSIS

Protocol Number: 10691	Product Names: VIR-7831 (Sotrovimab)
Title of Study: Pharmacokinetics of a SARS-CoV-2 Monoclonal Antibody in Hematopoietic Stem Cell Transplant Recipients	
PI: [name]	
Sponsor-Investigator: [name]	Phase of Development: Phase 1
Study Objectives: To assess the pharmacokinetics of the anti-SARS-CoV-2 monoclonal antibody (mAb) VIR-7831 up to six months post-transplant in hematopoietic stem cell transplant (HCT) recipients.	
Primary: To determine the levels of VIR-7831 mAb post-transplant in serum over time.	
Secondary: 

1. To compare the half-life of VIR-7831 in autologous vs. allogeneic transplant, cord vs. non-cord allogeneic transplant, matched vs mis-matched donors, in patients with and without GVHD, and in patients with and without diarrhea

2. To monitor the frequency of breakthrough SARS-CoV-2 acquisition in HCT recipients who have received VIR-7831

3. To compare antibody levels from serum collected by venipuncture versus self-collected using a TASSO device.

4. To monitor the development of anti-drug antibodies

5. To monitor safety with routine labs as part of standard post-transplant care.

6. Exploratory: To measure VIR-7831 and SARS-CoV-2 neutralizing antibodies in nasal swabs and SARS-CoV-2 neutralizing antibodies in serum.

	

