## 10. ADVERSE EVENT REPORTING

### 10.1 Definition of Adverse Events

**Adverse Event:** The International Council for Harmonization (ICH) guideline E6(R2) defines an AE as any untoward medical occurrence in a patient or clinical investigation subject administered a pharmaceutical product regardless of its causal relationship to the study treatment. An AE can therefore be any unfavorable and unintended sign (including an abnormal laboratory finding), symptom, or disease temporally related to the use of medicinal (investigational) product. The occurrence of an AE may come to the attention of study personnel during study visits and interviews or by a mAb recipient presenting for medical care.

AEs must be graded by the Principal Investigator or an authorized designee for severity and relationship to study product (see below). Severity can be assessed by a licensed clinician (i.e., physician, nurse, nurse practitioner, physician's assistant). Relationship to study product can only be assessed by a clinician licensed to make medical diagnoses (i.e., physician, nurse practitioner, physician's assistant) listed on the Form FDA 1572.

**Serious Adverse Event:** An SAE is defined as an AE meeting one of the following conditions:

- Results in death during the period of protocol-defined surveillance, except deaths that are the result of trauma or accident or the primary underlying malignancy.
- Is life-threatening (defined as a subject at immediate risk of death at the time of the event).
- Requires inpatient hospitalization or prolongation of existing hospitalization beyond the expected length of stay and during the period of protocol-defined surveillance. Hospitalizations for scheduled treatments, including scheduled admission for HCT are not SAE by these criteria.
- Results in a persistent or significant disability/incapacity.
- A congenital anomaly/birth defect.
- Any other important medical event that may not result in death, be life threatening, or require hospitalization, may be considered an SAE when, based upon appropriate medical judgment, the event may jeopardize the subject and may require medical or surgical intervention to prevent one of the outcomes listed above. Examples of such medical events include allergic bronchospasm requiring intensive treatment in an emergency room or at home, blood dyscrasias or convulsions that do not result in inpatient hospitalization, or the development of drug dependency or drug abuse.

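### A non-serious Grade 3 or higher chemistry abnormality that is only observed is not recorded as an adverse event, and no laboratory summary is planned

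*Combined protocol and SAP*

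**What the plan says.** Section 10.4 sets two recording rules in consecutive paragraphs. The general rule is that CRF entries "include any SAE or Grade 2 or above Adverse Event". The laboratory rule is that abnormal values of the tests the study specifies "should not be recorded as an adverse event unless an intervention is required (repeat testing to confirm the abnormality is not considered intervention". That sentence goes on to two further exceptions: "the laboratory abnormality results in a serious adverse event or the adverse event results in study termination or interruption/discontinuation of study treatment". It mentions neither grade nor dose.

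Section 10.1 says that an adverse event can be "any unfavorable and unintended sign (including an abnormal laboratory finding", with no condition about treatment. The synopsis words one secondary objective as "To monitor safety with routine labs as part of standard post-transplant care"; Section 3.2 shortens it to monitoring safety. Section 12.2 says only that routine safety laboratory tests will be monitored.

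Section 9.1 lists the tests reviewed from the medical record. They include creatinine, BUN, bilirubin, AST and alkaline phosphatase. Review takes place at infusion, weekly to week 4 and monthly to week 24. Under Section 6.1, treatment is one infusion of about 60 minutes. On the higher dose, Section 7 says: "There is currently no available PK or immunogenicity data on a 2000 mg IV dose".

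**The concern.** For laboratory results, the rule replaces severity with whether someone acted. A Grade 2 symptom is recorded, while a Grade 3 bilirubin that the team chose to watch is not. Routine laboratory tests are the means the synopsis names for the safety objective, yet the plan gives them no defined output apart from the adverse event record that this rule filters.

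What is at stake is how the safety results are read. Section 12.3 expects no safety signal, on the basis of a trial that used 500 mg. This trial gives 30 participants 2,000 mg. A report of few or no laboratory adverse events would fit that expectation, but a reader could not tell a true absence of abnormalities from an absence of recording.

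**Working it through.** The documents give no figure on this point, so there is none to reproduce. The check is textual, with one labelled illustration.

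**Step 1: apply Section 10.4 to typical cases.** All are assumed new or worsened since screening, because Section 10.4 does not record unchanged baseline conditions.

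| Case | Rule that applies | Recorded? |
|---|---|---|
| Grade 2 symptom, non-serious, untreated | Grade 2 or above | Yes |
| Grade 3 AST, non-serious, only watched, no diagnosis | Laboratory rule, no exception met | No |
| Grade 3 creatinine leading to an intervention | Intervention exception | Yes |
| Bilirubin rise that results in an SAE | SAE exception | Yes |
| Chemistry rise explained by a Grade 2 or higher diagnosis | Arguably an adverse event in its own right | Probably |
| Cytopenia needing an intervention, Grade 2 or above | Intervention exception | Yes |

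Only the second case is lost. It is the subject of this point.

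**Step 2: how far the other routes cover that case.**
- *Stopping or interrupting treatment.* Treatment ends after about 60 minutes, so a value found days later cannot interrupt it. Ending the study remains possible but would be unusual for a result that is only being watched.
- *Life-threatening SAE.* Section 10.1 requires an immediate risk of death. A Grade 3 or 4 laboratory value does not meet that automatically.
- *Important medical event.* Section 10.1 leaves this to medical judgment.
- *Diagnosis.* Section 10.4 has the investigator look for one from signs, symptoms and other clinical information. An isolated rise without symptoms may yield none.

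**Step 3: look for another output.** Section 12.2 describes no laboratory table, grade summary or shift analysis. Section 13.2 describes the safety content of the CRFs as reportable adverse events. The values remain in the medical record that Section 9.1 has the team review, but no section turns them into a result.

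**Step 4: illustration only.** Let p be the true proportion of participants with a Grade 3-4 laboratory abnormality, and s the share of those events that meet a recording exception. Both are assumptions; the documents give neither. With the 30 participants at 2,000 mg (Section 4) and independence assumed, the chance of at least one adverse event record is 1 - (1 - p × s)^30.

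| p | s = 1 | s = 0.5 | s = 0.25 |
|---|---|---|---|
| 5% | 1 - 0.95^30 = 78.5% | 1 - 0.975^30 = 53.2% | 1 - 0.9875^30 = 31.4% |
| 10% | 1 - 0.90^30 = 95.8% | 1 - 0.95^30 = 78.5% | 1 - 0.975^30 = 53.2% |

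The table shows direction: the fewer events that qualify, the less an empty record says. The conclusion does not depend on these rates.

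**The case against.** The best defence is that this is a deliberate and reasonable choice. Transplant recipients have many abnormal results, and recording them all would bury the useful ones. Recording rules are normally narrower than definitions: a non-serious Grade 1 event also meets Section 10.1 and is not recorded. The values are not lost either. Section 9.1 has them reviewed and Section 13.2 has the team meet at least weekly over recent data and adverse events. The primary objective is pharmacokinetic, and no liver or renal signal is documented. Section 7 reports no toxicity findings in monkeys up to the highest dose tested.

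Much of this stands. A reader might infer that Sections 10.1 and 10.4 contradict each other. They do not strictly: one says what can be an adverse event, the other what is entered. Surveillance is also not absent; what is missing is a recorded and summarised result.

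A reader might also infer that the rule keeps conditioning effects and removes drug effects. The documents do not support that. Intervention is left undefined except that repeat testing does not count, so treated chemistry changes qualify too, and nothing shows which cause prevails among the results left out.

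The defence does not explain why a Grade 3 chemistry result should need a higher bar than a Grade 2 symptom, or where the laboratory objective is reported. Limiting the change to four chemistry tests at Grade 3 or above answers most of the worry about noise.

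**Conclusion.** The point holds in limited form, as a gap in safety recording and reporting that should be closed. It does not affect the pharmacokinetic analysis. It covers results that are non-serious, Grade 3 or higher, untreated, without a separate diagnosis and without termination or interruption.

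Two stronger readings go too far. One is that laboratory values count only when treated, so that untreated Grade 3-4 values are never recorded. The SAE, termination and interruption exceptions and the diagnosis route rule that out. The other is that the problem belongs to 2,000 mg or to its first use. The rule applies equally to both doses, and the documents say only that pharmacokinetic and immunogenicity data are lacking at the higher dose, not that it has never been given.

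The number of affected results cannot be estimated, because no rate of untreated Grade 3 or higher chemistry abnormalities is given. The conclusion rests on reading Section 10.4 as written and on no separate laboratory summary being planned elsewhere.

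**What to change.** **Section 10.4.** Record Grade 3 or higher AST, bilirubin, alkaline phosphatase and creatinine results that are new or worse than baseline, whether or not anyone intervened. Keep the existing filter for blood counts and electrolytes.

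**Section 12.2.** Add a descriptive table of baseline grade against worst post-infusion CTCAE grade for these four tests, by dose cohort (500 mg and 2,000 mg), from the values already reviewed under Section 9.1. Name the baseline value, for example the last one before infusion. State two limits with the table:
- Testing follows a standard schedule to day +100 after transplant and is only as clinically indicated after that, so later abnormalities are found less evenly.
- The cohorts of 20 and 30 are sequential, small and exposed to conditioning, so differences cannot be attributed to drug or dose.

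**Cost.** Two changes of wording, one table and a few more CRF entries, with no new blood draws. Many added entries will be conditioning effects; the grade and test limits reduce them but do not remove them. Nothing in clinical management changes.
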